5.1.3.2 Last Visit

Last visit for endpoints assessed at clinic visits is defined as the last scheduled visit (not including the end of taper or safety follow-up visits) at which patient's last evaluation is performed.

5.1.3.3 Last 12 Weeks (OLE Only)

The last 12 weeks (84 days) of the OLE for IVRS based endpoints is defined as all available data from 12 weeks prior to the earliest of the date of the patient completing the OLE, or the last call to IVRS.

5.1.3.4 Treatment Period

The treatment period of the double-blind phase is defined as Day 1 to Day 113.

5.1.3.5 Titration Period

The titration period of the double-blind phase is defined as Day 1 to Day 28.

5.1.3.6 Maintenance Period

The maintenance period of the double-blind phase is defined as Day 29 to Day 113.

5.1.3.7 TSC-associated Seizures

TSC-associated seizures are defined as focal motor seizures without impairment of consciousness or awareness, focal seizures with impairment of consciousness or awareness, focal seizures evolving to bilateral generalized convulsive seizures, and generalized seizures (tonic-clonic, tonic, clonic and atonic) that are countable.

5.1.3.8 Other Seizures

Other seizures are defined as absence, myoclonic, partial (focal) sensory seizures, and infantile or epileptic spasms.

5.1.3.9 Total Seizures

Total seizures are defined as the combination of TSC-associated seizures and other seizures.

5.1.3.10 Focal Seizures

Focal seizures are defined as Type 1, Type 2 or Type 3 as follows:

- Type 1: focal motor seizures without impairment of consciousness or awareness.
- Type 2: focal seizures with impairment of consciousness or awareness.
- Type 3: focal seizures evolving to bilateral convulsive seizures.

5.1.4 Interim Analysis

No formal interim analysis is to be conducted in this trial. However, interim reporting of the OLE may be required to support regulatory filings. This SAP contains details for the final reporting of the double-blind and OLE phases of the trial. For interim reporting of the OLE,

the rules described in the SAP will be followed. However, only a subset of outputs including OLE data may be required to support regulatory filings.

If interim reporting of the OLE is required, then only data available up to and including the date of the data cut will be included. The below section describes how data will be selected for the interim reporting.

5.1.4.1 Selection of Data and Handling of Partial Dates

For data that has an associated visit date or date of collection but does not have an associated start or end date, there is expected to be no partial date information. Therefore, data of this type that are collected after the date of data cut will not be included as part of the interim analysis. For non-medical history data that have an associated start date or end date, such as AEs or concomitant medications, the following rules will be followed in order to determine whether the records are included in the interim analysis.

Partial Start and/or End Dates

The following procedures will be followed in the event that a record has partial start or end dates:

Partial start date:

- If the start date is partial, then it will be assumed to have started at the earliest possible date based on the partial date provided, for the purposes of determining if the data should be included in the interim analysis only.

Partial end date:

- If the end date is partial, then it will be assumed to have ended at the latest possible date based on the partial date provided. However, if the patient withdrew from the trial, completed the trial or died prior to this imputed date, then the maximum of the last available visit date and the withdrawal/completion or death date will be used instead.

Once the dates have been suitably imputed, the processes for complete start or end dates, specified below, can then be followed to determine whether the record should be included in the data cut and how it should be adapted.

Complete Start or End Dates

The following procedures will be followed in the event that a record has complete start or end dates:

- If the start date falls on or before the date of data cut and the end date falls after the date of data cut, then the record will be included in the data cut but the end date will be set to missing and depending on the type of data, the following adjustments will be made:
 - For an AE record, the outcome will be set to "Continuing".
 - For a concomitant medication record, the record will be set to "Ongoing at the End of the Trial".
- If the start date falls after the date of data cut, then the record will not be included in the data cut.

5.2 Analysis Sets and Protocol Deviations

5.2.1 Safety Analysis Set

All randomized patients who received at least 1 dose of IMP will be included and analyzed according to the treatment received. Only patients for whom it has been confirmed that they did not take any IMP will be excluded from this safety analysis set.

5.2.2 Intention to Treat Analysis Set

All randomized patients who received at least one dose of IMP will be included and analyzed according to their randomized treatment arm.

The intention to treat (ITT) analysis set is the primary analysis set for all efficacy endpoints.

5.2.3 Per Protocol Analysis Set and Protocol Deviations

If there are a sufficient number of significant protocol deviations in the trial, a PP analysis set may also be presented.

All patients who complete the trial with no protocol deviations deemed to compromise the assessment of efficacy, will be included and analyzed according to the treatment arm they were randomized. The rules determining the PP analysis set will be fully defined prior to unblinding of the database.

A listing will be produced of protocol deviations for the clinical study report. These protocol deviations will be imported from the protocol deviations log. Protocol deviations will be classed as minor, important or major, where major deviations are classed as important protocol deviations leading to exclusion from the PP analysis set.

Protocol deviations were reviewed during BDRMs on 22nd and 25th March 2019. In addition to patients in the ITT analysis set who withdrew from the trial during the blinded treatment phase, a number of patients were deemed to have protocol deviations that should lead to exclusion from the PP analysis set. These patients, together with their deviations, are detailed in a separate document finalized prior to unblinding.

5.2.4 OLE Safety Analysis Set

The OLE safety analysis set will be defined as all patients who receive at least one dose of IMP during the OLE phase of the trial. Only patients for whom it has been confirmed that they did not take any OLE IMP will be excluded.

5.3 Listings

All data will be listed and ordered by site, treatment, patient number and, where appropriate, chronological order of assessment. Listings will be created for each of the subsequent sections of the SAP.

Visit date need not be included on all of the listings, but day numbers will be included, where appropriate.

Other derived variables (e.g. changes from baseline values) that are calculated for analysis purposes or to aid interpretation of the data will be added to the listings as appropriate.

5.4 Demographic Data and Patient Characteristics

5.4.1 Patient Disposition

Patient disposition, by site, by country and overall, will be summarized using standard summary statistics. The number screened, number of screen failures and number randomized will be included.

A screen failure disposition table will be presented, including number of patients screened, number failing screening, number randomized and the reasons for failing screening.

Patient disposition for the double-blind and OLE phases, including patients treated, completed the treatment and taper phases, discontinued (including reason for discontinuation) from the treatment and taper phases will be summarized by absolute counts (n) and percentages (%).

A further table split by site, and by country will be produced, showing number of patients randomized, withdrawn and completed the treatment phase at each site or in each country

5.4.2 Analysis Sets

Patients included in the safety, ITT, PP and OLE safety analysis sets, and patients excluded together with reasons for exclusion, will be summarized by absolute counts (n) and percentages (%).

5.4.3 Demographic Data and Baseline Characteristics

The following demographic data will be summarized by treatment arm and overall for the safety, ITT, PP and OLE safety analysis sets:

- Age (years);
- Age group (1–6 years, 7–11 years, 12–17 years and 18–65 years);
- Sex;
- Race;
- Country;
- Region (US, Rest of the World);
- Weight at baseline (kg);
- Height at baseline (cm);
- Body mass index at baseline (kg/m²).

Age will be calculated as:

$$(\text{Date of screening} - \text{date of birth}) \div 365.25.$$

The following baseline characteristics will be summarized by treatment arm and overall for the safety, ITT, PP and OLE safety analysis sets:

- Average number of TSC-associated seizures per 28 days during baseline.
- Average number of total seizures per 28 days during baseline.
- Number of patients with seizures during the baseline period, by seizure type.
- Number of AEDs a patient has used, prior to the trial and is no longer taking.

- Number of AEDs a patient is currently taking.
- Total number of prior and current AEDs.
- Number of patients taking clobazam (Yes, No, and if no, Prior).
- Number of patients taking valproic acid (Yes, No, and if no, Prior).
- Number of patients taking levetiracetam (Yes, No, and if no, Prior).
- Number of patients taking vigabatrin (Yes, No, and if no, Prior).

The number of prior AEDs no longer taking will be taken from the 'History of antiepileptic medications and therapies' CRF page. The number of AEDs a patient is currently taking is based on the 'Concomitant antiepileptic medications' CRF page. If a patient has a medication listed on both the 'History of antiepileptic medications and therapies' and 'Concomitant antiepileptic medications' CRF pages and the medication is considered concomitant (see Section 5.7.1) for the double-blind phase, then this will not be included in the number of prior AEDs no longer taking. AEDs starting after the last dose of IMP during the double-blind phase will not be counted.

Patients taking the same AED type, but where the AED were coded to different generic terms will be counted only once within the AED type. For example, valproate sodium, valproic acid, valproate semisodium and ergenyl chrono will all be counted as valproic acid and counted once under that term.

The number of patients taking clobazam is defined as the number of patients taking clobazam at any point during baseline period or treatment period. The same definition will apply for the number of patients taking each of the other AEDs. The number of patients taking other AED types will also be presented if the overall frequency of patients taking the AED is >25%.

Previous cannabis use will be included within the baseline characteristics listing.

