## 8.3 Prohibited Therapy During Study Period

The following medications are prohibited for the duration of the study beginning from acquisition of patient consent/assent. However, any patients taking these medications after randomization should not be withdrawn from the study unless there are safety concerns. If applicable, the possible effects of these medications on the primary endpoint will be considered during the assessment of the evaluable period (see Section 13.6.1).

- Any new medications or interventions for epilepsy (including ketogenic diet and vagus nerve stimulation) or changes in dosage.
- Recreational or medicinal cannabis or synthetic cannabinoid-based medications (including Sativex®).
- Any other IMP taken as part of a clinical trial.

Care should be taken with drugs, or their metabolites, that are cytochrome P450 2C19 substrates, such as N-desmethylclobazam. Care should also be taken with drugs, or their metabolites, that are solely or primarily metabolized by UDP-glucuronosyltransferase 1A9 and 2B7.

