5.5.5 Subgroup Analyses

To assess the degree of effect heterogeneity, effect modifier analyses are proposed, on the ITT analysis set, for the primary efficacy endpoint and the key secondary efficacy endpoint of $\geq 50\%$ reduction in TSC-associated seizure frequency.

For the primary efficacy endpoint, the effect modifier analysis will be performed using the negative binomial regression analysis as described in Section 5.5.2. The model will be updated to include covariates for each level of the effect being tested (excluding a reference level), individually and with interactions with time, interactions with treatment arm and interactions with time and treatment. A separate model will be used for testing each effect. The treatment ratios (GWP42003-P vs. placebo), percent reduction and 95% confidence intervals will be presented for each level of the effect. In addition, the effect by time by treatment arm interaction p-value, testing the hypothesis that the effect level treatment ratios are homogeneous, will be presented.

For the key secondary efficacy endpoint of $\geq 50\%$ reduction in TSC-associated seizure frequency, patients with a $\geq 50\%$ reduction in seizure frequency will be modelled using logistic regression, including stratified age group and treatment arm as covariates. The model will also include covariates for each level of the effect being tested (excluding a reference level), individually and with interactions with treatment arm. A separate model will be used for testing each effect. The number and percent of responders, and odds ratios and 95% confidence intervals will be presented for each level of the effect. In addition, the effect by treatment arm interaction p-value, testing the hypothesis that the effect level odds ratios are homogeneous, will be presented.

The following effects will be tested:

- Age group (1-6 years, 7-11 years, 12-17 years and 18-65 years). Note: stratified age group will be removed as a covariate for this model.
- Sex (Male, Female).
- Region (US, Rest of the World).
- Clobazam use (Yes, No).
- Valproic acid use (Yes, No).
- Levetiracetam use (Yes, No).
- Vigabatrin use (Yes, No).
- Baseline average TSC-associated seizures per 28 days (\leq observed Tertile 1, $>$ observed Tertile 1 to \leq observed Tertile 2, $>$ observed Tertile 2). The observed tertile values will be rounded to the nearest whole number.
- Number of concurrent AEDs (<3 , ≥ 3).
- Number of prior AEDs (<5 , ≥ 5).

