- Number of prior and concurrent AEDs (<8 , ≥ 8).

Effects of patients taking other AED types will also be tested if the overall frequency of patients taking the AED is $>25\%$.

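### AED-use and AED-count effect modifiers rest on a definition that runs through the treatment period, so subgroup membership can depend on outcome; the likely bias is small and confined to supportive analyses

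*SAP*

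**What the plan says.** SAP 5.4.3 (Demographic Data and Baseline Characteristics) places clobazam, valproic acid, levetiracetam and vigabatrin use, and the number of current AEDs, among the baseline characteristics. It defines a clobazam user as a patient "taking clobazam at any point during baseline period or treatment period" and adds: "The same definition will apply for the number of patients taking each of the other AEDs". SAP 5.1.3.4 fixes the period: "The treatment period of the double-blind phase is defined as Day 1 to Day 113". For the counts, the only exclusion is "AEDs starting after the last dose of IMP during the double-blind phase will not be counted".

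SAP 5.5.5 (Subgroup Analyses) begins: "To assess the degree of effect heterogeneity, effect modifier analyses are proposed, on the ITT analysis set, for the primary efficacy endpoint", and adds the ≥50% responder endpoint. Its list includes "Clobazam use (Yes, No", the other three named AEDs in the same form, and three count variables (concurrent <3 or ≥3, prior <5 or ≥5, prior plus concurrent <8 or ≥8). It continues: "Effects of patients taking other AED types will also be tested if the overall frequency of patients taking the AED is" above 25%. It gives no time point and no reference to 5.4.3.

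Protocol 8.2 does not allow new AEDs in the randomized phase, and Protocol 10 lists adding one as a reason for which a patient may be withdrawn. Protocol 8.3, however, says of prohibited therapy that "any patients taking these medications after randomization should not be withdrawn from the study unless there are safety concerns".

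**The concern.** A subgroup variable should be fixed before treatment can influence it. Here a patient who was not on an AED at randomization, whose seizures worsen and who is then given that AED, is classed as a user and takes the poor outcome into the user subgroup. If the drug works, this happens more often on placebo. With no true effect modification, the treatment effect then looks larger among AED users and smaller among non-users.

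Seven of the eleven listed effects draw on AED data: four named drugs and three counts. Even the count of prior AEDs is exposed, because under 5.4.3 a previously stopped AED that becomes concomitant leaves the prior count. Whether the effect differs by co-medication is a natural question for an add-on therapy, and a modifier that can depend on outcome makes any answer contestable.

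**Working it through.** **1. How the definition reaches 5.5.5.** The two sections share the same four AEDs, the same Yes/No coding and the same 25% threshold for adding others. No other definition of AED use appears in the SAP. The link is an inference, but someone programming 5.5.5 has nothing else to use.

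**2. Whether on-treatment starters remain in the data.** Protocol 8.3 keeps them in the study. Protocol 13.6.1 ends the evaluable period the day before a relevant AED change. The SAP does not carry this cut over: its treatment period is Day 1–113, and 5.1.1.1 uses all available data, including data after withdrawal. Even with the cut, subgroup membership would still be set by the later AED.

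**3. The plan's design figure.** The documents give no figure on this point. The sample-size inputs (SAP 3.2: 15% and 50% mean reductions, SD 60%, 70 per arm) do reproduce. By Noether's formula, p = Φ(35/(60√2)) = 0.660; total N = (1.960 + 1.282)²/(3 × 0.160²) = 136.8, or 69 per arm; power at 70 per arm is Φ(√420 × 0.160 − 1.960) = 0.906, against the stated 90%.

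**4. Size of the bias.** Let the log ratio of treatment-period to baseline seizure rate be normal, with mean m = ln 0.85 = −0.1625 on placebo and ln 0.50 = −0.6931 on active. The true active/placebo ratio is then 0.50/0.85 = 0.588 in every subgroup. Assumptions not in the documents: SD s of 0.6 or 0.9, baseline use b of 26% or 40%, and a fraction f of non-users with a rising seizure rate who start the AED. With q = 1 − Φ(−m/s) and e = m·q + s·φ(m/s), the subgroup means in each arm are

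- *No*: (m − f·e)/(1 − f·q)
- *Yes*: (b·m + (1 − b)·f·e)/(b + (1 − b)·f·q)

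Example with s = 0.6, b = 0.26, f = 0.10:

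- Placebo: q = 0.3932, e = 0.1668; *No* mean −0.1865, *Yes* mean −0.1035; starters per 70 = 70 × 0.74 × 0.10 × 0.3932 = 2.0.
- Active: q = 0.1240, e = 0.0369; *No* mean −0.7056, *Yes* mean −0.6594; starters per 70 = 0.6.
- Ratios: *No* exp(−0.7056 + 0.1865) = 0.595; *Yes* exp(−0.6594 + 0.1035) = 0.574.

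Over all four combinations of s and b:

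| f | Placebo starters per 70 | Active starters per 70 | Ratio, *Yes* | Ratio, *No* |
|---|---|---|---|---|
| 2% | 0.3–0.4 | 0.1–0.2 | 0.585–0.587 | 0.589–0.590 |
| 10% | 1.7–2.2 | 0.5–1.1 | 0.574–0.582 | 0.594–0.595 |
| 25% | 4.1–5.5 | 1.3–2.9 | 0.561–0.576 | 0.605–0.608 |

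With use defined at baseline, both ratios stay at 0.588.

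**5. Interaction test.** In simulation (70 per arm, SD 0.9, 26% baseline use, f from 2% to 25%, 6,000 trials each), a z-test of the interaction on log ratios rejected in 5.4–6.2% of trials with the any-time definition and 5.3–5.9% with the baseline definition. The Monte Carlo standard error is √(0.055 × 0.945/6000) = 0.3 percentage points. A second simulation (SD 0.75, 30% baseline use, starting only after a rise above 30%, 4,000 trials each) gave 6.0%, 6.4% and 10.3% at start rates of 10%, 25% and 50%, against about 5–6%. Its *No*/*Yes* ratios were 0.60/0.58, 0.61/0.56 and 0.64/0.54. The 50% setting needs about 7 of 70 placebo patients to start the same AED.

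**The case against.** The strongest reply has four parts.

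First, 5.5.5 does not cite 5.4.3, whose sentence defines a row of a descriptive table. A reader might infer that the SAP expressly assigns subgroups by on-treatment use. It does not: the link is the only available reading, not a stated rule. If baseline use was intended, 5.5.5 still needs to say so.

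Second, the mechanism runs mainly through protocol deviations. AEDs must stay stable, and new ones are barred in the blinded phase. Protocol 8.3 is a contingency rule and gives no expected frequency, so a reader should not take it as a forecast that many AEDs will be added. This limits the size of the problem but does not remove it, because those patients stay in the analysis. Protocol 8.3 and the optional withdrawal in Protocol 10 need reconciling, but the point does not depend on which governs.

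Third, the calculations cover one Yes/No factor on a log-ratio scale. They do not model the negative binomial mixed model, the responder endpoint, the AED counts or any benefit from the added drug. That stands: they show direction and scale only.

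Fourth, for treatment-emergent transaminase elevations in SAP 5.6.3.1, co-exposure during treatment is a defensible grouping. That also stands, and those subgroups need not change.

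**Conclusion.** The point holds in a limited form. As written, the plan supplies a definition of AED use and AED count that includes post-randomization starts, labels it baseline, and leaves it as the only one available to the effect-modifier analyses. Membership can then depend on outcome.

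The likely effect is small: about 0.01–0.03 on a subgroup ratio whose true value is 0.59, at assumed start rates of 10–25% among worsening non-users, and less if additions are rarer or spread over several AEDs. A reader might go further and infer that the interaction tests are seriously inflated, or that the primary and responder results are biased. Neither follows. Interaction rejection hardly moves at those start rates and rises clearly only at 50%, a rate for which the documents give no support. The subgroup analyses lie outside the eight-step hierarchy in SAP 5.5.1, and AED use is not a term in the primary model or the responder test.

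The change is still worth making, because it removes an avoidable objection to any AED interaction that is reported.

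**What to change.** In SAP 5.4.3 and 5.5.5, define AED use (each named AED and any other above 25%) and number of concurrent AEDs as AEDs started before Day 1 and ongoing at the first dose of study medication. Have 5.5.5 refer to that definition, and derive the prior and combined AED counts consistently with it. Handle partial or missing dates by the conventions already in SAP 5.1.1.4 and 5.7.1. Keep any-time use as a descriptive concomitant-medication summary. The liver subgroups in 5.6.3.1 may keep on-treatment exposure, but should say so.

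The cost is a sentence or two in the SAP and one date condition in the derivation. SAP 5.7.1 already derives start and stop days for medications, so no new data are needed.

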5.4.4 Epilepsy History

5.4.4.1 Genetic Testing History

Genetic testing history data will be listed only.

5.4.4.2 History of Seizures no Longer Occurring and History of Current Seizures

Data will be summarized by treatment arm and overall for the safety analysis set only, separately, for history of seizures no longer occurring and history of current seizures.

The following will be summarized by each seizure type:

- Number of patients with the seizure type.
- Age at onset (years).
- Age of last occurrence (years). For history of seizures no longer occurring only.
- Seizure duration (<2 minutes, 2–10 minutes, >10 minutes, Unknown). For history of current seizures only.

Seizure frequency data will be listed only.

For patients with more than one record for a particular seizure type, the earliest onset, most recent age of last occurrence and longest duration will be used for the summary table.

